1.5 Safety of L-citrulline

L-citrulline is a naturally occurring amino acid. It is produced by, and normally present in, the human body. Typical circulating levels of citrulline in adults are 16-55 µmol/L. In children <12 years of age, the levels are 16-32 µmol/L. Oral citrulline has been used for years as a food supplement to enhance energy and prevent muscle fatigue and has been found safe in doses of 2-15 g, which is a multiple of the administered dose in the L-citrulline trials conducted to date (http://examine.com/supplements/citrulline/ #summary_full) (Moinard, Nicolis et al.

2008).

No SAEs occurred in the oral citrulline study reported by Smith, Canter et al. 2006. Four adverse reports were submitted to the Institutional Review Board (IRB) per protocol on patients who developed hypotension secondary to surgical complications and required further surgical or medical support. These cases were reviewed and determined to not be related to study drug administration.

In the first report of the use of L-citrulline in humans, L-citrulline was found to be both safe and well tolerated (Barr, Tirona et al. 2007). One patient required advanced life support following a junctional rhythm postoperatively and profound bradycardia consistent with complete heart block. The patient recovered fully. The Data Safety Monitoring Board (DSMB) reviewed the event and deemed it not likely related to L-citrulline.

Serious AEs (SAEs) under L-citrulline treatment in the Vanderbilt pilot study included postoperative bleeding (2 patients), and obstructive airway disease (1 patient). Although these events occurred in 3 out of 35 L-citrulline patients only, these types of adverse events (AEs) will be monitored in future studies.

Safety data from the completed CIT-002-01 study have shown that of the patients randomized and treated, all patients (100%) in the i.v. L-citrulline group and 73% of patients in the placebo group experienced at least one AE. AEs that were judged to be related to study treatment were reported in the placebo group (2 patients, 18%), but not in the active treatment group. No AE leading to death and no other SAE was reported in this study. No AE leading to treatment discontinuation was reported.

1.6 Rationale for the study

Asklepion intends to develop L-citrulline for the prevention of clinical sequelae of acute lung injury induced by CPB in pediatric subjects undergoing surgery for congenital heart defects. Cardiopulmonary bypass causes a transient systemic inflammatory response leading to clinical manifestations of acute compromise of cardiovascular and pulmonary function requiring extended mechanical ventilation and use of inotropes (Kozik and Twedell 2006).

Pediatric patients undergoing congenital heart defects surgery are most vulnerable to experiencing lung injury sequelae during the immediate postoperative period. CPB-induced acute lung injury represents a complex interplay between the preoperative condition of the patient (importantly age at repair, type of lesion and clinical manifestations) and the inevitable disruption in the endocrine and vasoactive peptide milieu that results from cardiac surgery. L-citrulline, with its mechanism of action, is intended as a preventive treatment to improve restoration and maintenance of normal vasodilation, thus improving clinical status and reducing the need for-and exposure to-mechanical ventilation and inotrope treatment.

The reduction of key manifestations of acute CPB-induced lung injury, namely the postoperative need for mechanical ventilation and for inotrope therapy will provide evidence for Lcitrulline's intended clinical effect.

2 Study Objectives

2.1 Primary Objective

The primary objective of the study is to determine if L-citrulline delivery given perioperatively reduces clinical sequelae of acute CPB-induced lung injury in pediatric subjects undergoing repair of congenital heart defects, as evidenced by the reduction of post-operative need for mechanical ventilation and inotrope therapy.

2.2 Secondary Objective(s)

Secondary objectives are to evaluate the effect of L-citrulline compared with placebo regarding

- safety and tolerability
- hemodynamic improvement post-operatively
- the usage and length of time on vasodilators
- length of hospitalization

- the duration of chest tube placement
- the plasma concentrations of citrulline

3 Study Endpoints

3.1 Primary Endpoint

A composite variable consisting of the longer of either (1) length of time on mechanical ventilation or (2) length of inotrope use.

The definition of mechanical ventilation shall include invasive mechanical ventilation or non-invasive mechanical ventilation including bi-level (biphasic) positive airway pressure (BPAP) or continuous positive airway pressure (CPAP).

3.2 Secondary Endpoints

3.2.1 Secondary Efficacy Endpoints

- Length of time on mechanical ventilation
- Length of time on positive pressure ventilation
- Length of time of inotrope use
- Inotrope score calculated each hour post-operatively from the time of separation from bypass until the completion of study drug; additionally, the total inotrope score over time until Day 28 or hospital discharge will be derived
- Hemodynamic improvement (heart rate, systemic arterial blood pressure, oxygen saturation, and central venous pressure)
- Thoracotomy output; duration and volume of chest tube drainage
- Length of time of intubation
- Length of PICU stay
- Length of time on vasodilators
- Length of hospitalization
- Plasma concentrations of citrulline

3.2.2 Secondary Safety Endpoints

- Occurrence of adverse and serious adverse events
- Incidence of refractory hypotension
- Change from baseline in laboratory values (serum electrolytes, blood urea nitrogen [BUN], creatinine, complete blood count [CBC] with differential, activated clotting time [ACT] & liver enzymes)

4 Investigational Plan

4.1 Overall Study Design and Plan

This is a multicenter Phase III double-blind, randomized, placebo controlled study to evaluate the efficacy and safety of L-citrulline for the prevention of clinical sequelae of acute lung injury induced by CPB in pediatric subjects undergoing surgery for congenital heart defects.

Children undergoing repair of cardiac defects that include a large unrestrictive VSD or a partial or complete AVSD or an ostium primum ASD will be eligible for enrollment in this study.

• 190 subjects will be randomized in a 1:1 fashion to either L-citrulline or placebo. L-citrulline treatment will include: 1) an L-citrulline bolus of 150 mg/kg or placebo at the initiation of CPB, but after removal of any crystalloid base; 2) the addition of L-citrulline at a concentration of 200 µmol/L or placebo given as a bolus during bypass. This may be administered as a one-time bolus or multiple administrations to compensate for fluids containing L-citrulline that may be removed from the patient during the course of the operation and thus to maintain the concentration of 200 µmol/L; and 3) an L-citrulline bolus of 20 mg/kg or placebo 30 minutes after decannulation from CPB immediately followed by a 9 mg/kg/hr continuous infusion of L-citrulline or placebo for 48 hours (see Section 4.4.1 for further details). The study drug or placebo infusion will be discontinued once invasive arterial blood pressure monitoring is discontinued or at 48 hours, whichever comes first. Subjects will be followed until discharge from the hospital, and a final assessment via telephone will be conducted at Day 28.

4.2 Discussion of Study Design

This study will examine patients who develop significant sequelae of CPB-induced lung injury

in the absence of confounding co-morbidities. Consequently, secundum ASDs are excluded because they are often clinically insignificant and patients with secundum ASDs rarely develop significant clinical sequelae of CPB-induced lung injury. Inclusion of the very common secundum ASDs would thus dilute study results. Similarly, single ventricle defect patients are excluded because of their high incidence of co-morbidities that would prolong the use of positive pressure ventilation and inotrope usage by confounding mechanisms other than CPB-induced lung injury.

A primary concern in designing a study to confirm that perioperative administration of L-citrulline to CPB patients does indeed provide a substantive clinical benefit is to construct an endpoint or endpoints that are reliable and consistent.

The following factors underlie the determination of the appropriate primary endpoint for the proposed trial: there is consistent pathophysiology among pediatric congenital heart defect patients receiving CPB: pulmonary endothelial insult and disruption => CPB-induced acute lung injury => increased vascular resistance and elevated vascular pressure => various morbidities and risks, including congestive heart failure => prolonged ICU stays with continued positive pressure ventilation and inotrope therapy.

Each patient will be randomized to receive either L-citrulline or placebo for the duration of the study. Randomization will be performed using a previously generated randomization scheme, and stratified by site to ensure, to the extent possible, equal randomization into both treatment arms.

The study is double-blinded for all investigational staff who make determinations related to the study, with the sole exception of the hospital or site pharmacist who will be single-blind in order to properly prepare the individual subject's medication (see Section 4.4.7).

4.3 Selection of Study Population

4.3.1 Number of Planned Subjects

Approximately 450 subjects will be screened to obtain 190 patients randomized to either placebo or L-citrulline in a 1:1 ratio. A total of approximately 190 subjects are anticipated to complete the study.

The estimated enrollment period is 11 months. The total trial period for a patient is up to 42 days (up to 2 weeks screening, 2 days treatment, up to 28 days follow-up). The trial end is defined as "last patient out" (LPO).

4.3.2 Inclusion Criteria

To be eligible for study entry subjects must satisfy all of the following criteria:

- Subjects, parents, or legal guardian of the subject who are willing and able to sign informed consent
- Male and female subjects aged ≤18 years of age (females of child-bearing potential must be willing to practice an acceptable form of birth control; i.e. oral contraceptive, hormonal implant; etc.)
- Infants, children and adolescents undergoing CPB for repair of a large unrestrictive VSD, an ostium primum ASD, or a partial or complete AVSD
- Pre-operative echocardiogram which confirms the cardiovascular anatomy and defect to be surgically repaired

4.3.3 Exclusion Criteria

Subjects will be excluded from the study if one or more of the following statements are applicable:

- Evidence of pulmonary artery or vein abnormalities on the pre-operative echocardiogram that will not be addressed surgically. Specific abnormalities excluded include the following:
 - Significant pulmonary artery narrowing not amenable to surgical correction
 - Previous pulmonary artery stent placement
 - Significant left sided AV valve regurgitation not amenable to surgical correction
 - Pulmonary venous return abnormalities not amenable to surgical correction
 - Pulmonary vein stenosis not amenable to surgical correction
- Preoperative requirement for mechanical ventilation or i.v. inotrope support
- Presence of fixed or idiopathic pulmonary hypertension (i.e. Eisenmenger's Syndrome) prior to surgical repair
- Pre-operative use of medications to treat pulmonary hypertension
- Pregnancy; Sexually active females of child-bearing potential must be willing to practice an acceptable method of birth control for the duration of study participation

(e.g. oral contraceptive, hormonal implant, intra-uterine device)

- Participation in another clinical trial within 30 days of Screening or while participating in the current study, including the 28 days of follow-up post study drug administration.
- Any condition which, in the opinion of the investigator, might interfere with the study objectives

4.3.4 Removal of Subjects from Therapy or Assessments

The person(s) providing consent is free to withdraw his/her consent regarding participation in this study at any time, for any reason, specified or unspecified and without penalty or loss of benefits to which the subject is otherwise entitled.

Subjects may be withdrawn from the study by the Investigator at any time due to an AE or for any other reason if it is in the opinion of the Investigator that continued participation in the study is no longer in the best interest of the subject. These reasons include, but are not limited to the following:

- Adverse drug reaction or AE or any other reason for which, in the opinion of the Investigator, subject's continued participation in the study is not in the best interest of the subject
- Serious protocol violation(s), such as determination of fulfilment of exclusion criteria during surgery only
- Lack of response of subject or subject's parents/legal guardian to the attempts of the investigational site to contact him/her (lost to follow-up)

The reason(s) for withdrawal must be documented in the case report form (CRF).

For subjects withdrawing or being withdrawn from the study, it will be encouraged to have the same final evaluations completed as those for subjects completing the study according to this protocol, particularly safety evaluations.

For subjects who are lost to follow-up, reasonable efforts will be made to contact the parents or legal guardians of subjects, or the subjects themselves if they provided their own consent. These efforts must be documented in the subject's file.

Subjects who have been randomized and who withdraw or are withdrawn for any reason will not be replaced.

The sponsor has the right to terminate the study at any time in case of SAEs or if special circumstances concerning the investigational medicinal product (IMP) or the company itself occur, making further treatment of subjects impossible. In this event, the investigator(s) will be informed of the reason for study termination.

4.4 Investigational Medicinal Products

4.4.1 Investigational Medicinal Products Administered

The main objective of the dosing schedule, as outlined below, is to achieve a minimum systemic target plasma trough level concentration of 100 μ mol/L of L-citrulline to provide the most beneficial effect as demonstrated in the previous phase 2 study. As a general guiding principal during bypass, once dosing has begun, all fluids entering the circuit must contain 200 μ mol/L of L-citrulline in order to achieve and maintain the trough level of 100 μ mol/L of L-citrulline. Therefore, if fluids are being added or removed, it is crucial to take this into consideration when timing the administration of the required doses. The following section describes the administration of L-citrulline or placebo, while taking into account the above objective.

- The first (initial) dose administered will be an L-citrulline bolus of 150 mg/kg or placebo, administered at the initiation of CPB, but after removal of any crystalloid base.
 - If fluid is added to the priming circuit, but removed prior to initiation of bypass, then the initial 150 mg/kg bolus dose should be added after the crystalloid based fluids are removed and at the initiation of bypass.
 - If fluid is added to the priming circuit, but not removed, then the initial 150 mg/kg dose should be added to the circulating prime used for the bypass.
- The second dose administered consists of L-citrulline at a concentration of 200 µmol/L or placebo, given as a bolus during bypass. This may be administered as a one-time bolus or multiple administrations, to maintain the concentration at 200 µmol/L. The total dose will be dependent upon the total amount of any volume administered and removed during CPB. This includes the crystalloid portion of the cardioplegia so as not to dilute the loading dose; it is significantly important when using a hemoconcentrator.
- The third dose administered will be a bolus of 20 mg/kg of L-citrulline or placebo, administered 30 minutes after decannulation from CPB.

 The above third dose is immediately followed by a 9 mg/kg/hr continuous infusion of L-citrulline or placebo for up to 48 hours. The study drug or placebo infusion will be discontinued once invasive arterial blood pressure monitoring is discontinued or at 48 hours, whichever comes first.

Placebo will be matched for volume using suitable fluid recognized as standard of care for such procedure (e.g. normal saline or Plasmalyte without L-citrulline added).

All study medications will be prepared and provided by each site's investigational pharmacy. A pharmacy manual will be provided to the hospital or institution Investigational Pharmacist. The manual will contain detailed instructions for the preparation of the investigational product. The manual will include specific directions on randomization procedures, preparation of study drug or placebo and labeling of product for administration. The label should contain subject information (e.g. subject initials, subject identification number), study number, volume of product to be administered, and the date of administration. However, the label may not contain any information that identifies the actual product being administered.

All study medications will be administered by the Investigator or by medically trained personnel under his/her supervision (e.g., the anesthesiologist, perfusionist, PICU personnel, etc.).

Doses will be given by a central i.v. catheter that will be emplaced after induction of anesthesia or via the bypass circuit. Separate i.v. access is not required for the study drug. The study drug is isotonic and can run through either a peripheral i.v. or a central venous catheter at the discretion of the clinical staff. The study drug is an amino acid (or placebo) and thus, for compatibility purposes, the drug product is treated like parenteral nutrition. Additionally, it is compatible with fluids used for filtration or hemoconcentration during CPB.

No dose adjustments will be allowed; however, study drug may be discontinued as noted above.

4.4.2 Identity of Investigational Medicinal Products

The L-citrulline drug product is a sterile, non-pyrogenic injectable clear solution intended for intravenous administration. It is supplied as a 10 mL, single use vial containing 500 mg L-citrulline in 10 mL of acidified water. The product is packaged in a clear glass vial (13 mm neck) with a grey stopper and blue flip-off cap/aluminum seal. The L-citrulline drug product is manufactured aseptically at a concentration of 50 mg/mL using fully synthetic drug substance dissolved in water for injection. The resulting solution pH is adjusted to near pH 3, sterile filtered and filled.

Study drug should be stored as instructed: Store at 2-8°C (36-46°F); do not freeze.

The drug product is manufactured and imported according to current Good Manufacturing Practice and the relevant regulatory requirements.

4.4.3 Packaging and Labeling

L-citrulline study drug comes in a clear glass vial (13 mm neck) with a grey stopper and blue flip-off cap/aluminum seal. Boxes of 25 vials are supplied to the study centers.

The batch number, strength, storage conditions, and federally required language stating that the product is "for investigational use only" or "for clinical trial use only" will be printed on the outer package. A Material Safety Data Sheet (MSDS) will be provided with the shipment.

All packaging and labeling operations will be performed according to the current Good Manufacturing Practice for Medicinal Products and the relevant regulatory requirements.

4.4.4 Method of Assigning Subjects to Treatment Groups

Screened subjects will be assigned a unique 5-digit number, with the first two digits identifying the site and the next three digits identifying the subject, e.g. 01-001. At each site, the investigator will assign numbers to subjects in ascending order (e.g. 001, 002, 003).

Eligible subjects will be randomized to a treatment (placebo or L-citrulline) in a 1:1 ratio. Randomization will be performed per study site via an interactive web response system (IWRS). The randomization schedule will be generated using a validated randomization program. A unique randomization number will be assigned to each randomized subject. Randomization assignment will be stratified at each site to ensure balance of the number of randomized subjects to both treatment groups.

4.4.5 Selection of Doses in the Study

Initial supplementation trials utilized oral citrulline at a dose of 1.9 g/m² per dose, administered before CPB, postoperatively upon admission to the intensive care unit and every 12 hours at hour 12, 24 and 36. Oral citrulline was well tolerated with no evidence of significant AEs. In addition, it was noted that patients who had a 12-hour plasma citrulline level >37 μ mol/L (the upper range of normal levels) did not develop increased PVT. Unfortunately, not all patients receiving oral citrulline reached these levels (Smith, Canter et al. 2006).

In a dose escalation study targeting a sustained plasma level of approximately 100 μ mol/L, it was noted that L-citrulline has a fairly short half-life, thus requiring a classic bolus and continuous infusion drug delivery protocol (Barr, Tirona et al. 2007). A subsequent study (CIT-002-01) confirmed that the following L-citrulline administration would result in sustained plasma L-citrulline levels of approximately 100 μ mol/L:

- An L-citrulline bolus of 150 mg/kg or placebo at the initiation of CPB
- The addition of L-citrulline at a concentration of 200 µmol/L or placebo to both the bypass circuit priming fluid as well as to the hemofiltration fluid utilized during CPB
- A bolus of L-citrulline of 20 mg/kg or placebo, 30 minutes after decannulation from CPB, immediately followed by initiation of a 9 mg/kg/hr continuous infusion of Lcitrulline or placebo for 48 hours

This treatment regimen, with clarification added for the dose(s) given during bypass, will also be used in the current study.

4.4.6 Drug Accountability

The Pharmacist at the study site is responsible for keeping accurate drug accountability records throughout the study regarding the receipt of study drug, the preparation of study drug and dispensation to subjects, and the reconciliation of all used and unused study drug.

All empty and partially used vials should be retained by the pharmacy in order for study drug accountability to be performed. The total amount of study drug prepared for administration to the patient will be calculated by the investigational pharmacist, with verification of the calculations performed by a second qualified person (e.g. pharmacy technician). Total volume of study drug administered to the patient will be documented in the source documents and in the electronic case report forms (eCRFs).

A Drug Preparation Log as well as a Drug Dispensing and Accountability Log must be kept current and must contain the following information:

- Batch number
- Subject number for whom the drug was prepared
- Date on which drug was dispensed
- Quantity of the drug administered

4.4.7 Blinding

Randomization will take place via an IWRS system. The site's investigational pharmacist will be responsible for obtaining the randomization assignment. Therefore, the site pharmacist will only be aware of the treatment assigned to each individual subject. The pharmacist has no other role in the study other than preparing the study product. Study drug or placebo will be prepared and labeled with the appropriate subject identifiers; however, no information that would reveal the actual contents of the dose to be administered (active vs. placebo) will be included on the label. Study drug will be provided in either syringes or bags and mask-labeled. Placebo is also mask-labeled and provided in either syringes or bags. The bags are the same size, shape, and fluid clarity, and hence masked to both investigators and staff (if other than the investigator) administering the drug. Therefore, the investigator and staff administering the product will remain blinded as to its contents. Only the pharmacist and the unblinded monitor responsible for performing drug accountability (a different monitor than the person performing routine data monitoring) will be aware of the treatment assignment.

Data may be unblinded at the request of the DSMB to the study Medical Monitor in the event that a safety issue arises for which they determine there is a need to review the subject's treatment assignment. If data is unblinded for any reason, the DSMB will not share the treatment assignment with the Sponsor, unless there is a medical or ethical reason to do so.

The randomization assignment should not be revealed before the study has been completed and the database has been cleaned and closed. The study will be unblinded using a study specific unblinding procedure.

In rare emergencies, such as the investigator feels adequate treatment of an AE requires knowledge of study treatment, unblinding of an individual subject may be necessary. In case of an emergency, the treatment administered to the subjects can be revealed using the unblinding function of the IWRS.

In such events, the Investigator must make every attempt to inform the study Medical Monitor before breaking the blind or as soon as possible after unblinding has been performed (within 24 hours after the emergency unblinding). The date, time and reason for breaking the code, the treatment administered (placebo or L-citrulline), and the sponsor's representative who was informed of the unblinding, will be documented within the eCRF/IWRS.

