Based on available data with L-citrulline treatment, there are no anticipated risks or side effects. The only potential AE would be transient systemic arterial hypotension.

Unexpected Adverse Events

An unexpected adverse event is any adverse event that has not been previously described in available risk information (included in the protocol or the investigator's brochure).

Reporting of Adverse Events

All AEs occurring during the study must be documented on the relevant CRF pages. Non-serious AE's will only be recorded in the CRF. Serious AE's will be recorded in the CRF and

Asklepion GROWTH HEALTH INNOVATION

11 August 2017

also reported to the CRO. SAEs must be reported by the investigator if it occurs during the clinical study or within 30 days of the patient receiving the IMP, whether or not the SAE is considered to be related to the IMP.

SAEs must be reported within 24 hours to the following:

[name]

FGK Clinical Research GmbH

[name]

Toll-free [contact]

P: [name] F: [name] Email: [contact] Cc: [contact]

The investigator should not wait to receive additional information to document the event before notification of an SAE, although additional information may be requested. Where applicable, information from relevant laboratory results, hospital case records, and autopsy reports should be obtained.

SAEs must be followed until resolution or death, including those still ongoing at the Follow-up visit.

The CRO Medical Monitor must, in turn, forward the SAE report to the Asklepion Chief Medical Officer (CMO) as soon as is reasonably possible, but in any case, within 24 hours of receipt from the site. The CRO Medical Monitor or designee will notify the participating Institutional Review Board(s) (IRBs)/Ethics Committee(s), and CMO will notify the DSMB as appropriate.

SUSAR (Suspected Unexpected Serious Adverse Reaction)

A SUSAR is a serious adverse event that is suspected to be at least possibly related to the investigational drug (per the definitions of Causality in this section) and Unexpected (per the preceding definition of expectedness).

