7.4 Interim Analysis

One interim analysis is planned to be carried out when the first 95 consecutively randomized full analysis set (FAS)-patients (i.e. 50% of the planned patients) will have undertaken their Follow up visit (Day 28 or Hospital Discharge), data required for the analysis of the composite endpoint have been entered into the eCRF, and those data have been cleaned appropriately. Only a sample size re-estimation will be carried out during this interim analysis; no other statistical analyses will be conducted. The sample size re-estimation will be done by an independent, unblinded statistician following the same procedures and criteria as for the initial

sample estimate, as described in section 7.2. Only the results of the sample size re-estimation will be provided to Asklepion.

Only the re-estimated variance values will be used for sample re-calculation, while the assumed values will not be re-estimated but kept as described in Section 7.2.

In the event that the sample size re-estimation leads to a reduction of the sample size due to lower re-estimated variance compared to the assumed variance values, the sample size as currently planned will be kept, and not reduced, to ensure robust estimations for safety and efficacy variables.

If the trial is to be continued with the re-estimated sample size, an appropriate protocol amendment will be submitted to the FDA as soon as feasible.

Final analysis will be based on the population of all randomized patients without taking the sample size re-estimation results into consideration. Due to the fact that only the interim variance will be assessed, no alpha adjustment of statistical analyses is required.

8 Quality Assurance and Quality Control

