9.2 Financing and Insurance

Financing and insurance of this study will be outlined in a separate agreement between CRO and the sponsor.

10 Data and Safety Monitoring Board

The Data and Safety Monitoring Board (DSMB) will act in an advisory capacity to the Coordinating Investigator and Asklepion Pharmaceuticals, LLC to monitor participant safety. The DSMB responsibilities are to:

- Protect the safety of the study participants;
- Review the research protocol and plans for data safety and monitoring;
- Evaluate participant risk versus benefit, and other factors that can affect study safety outcome;
- Consider factors external to the study when relevant information becomes available, such as scientific or therapeutic developments that may have an impact on the safety of the participants or the ethics of the trial;
- Report to the study sponsor, Asklepion Pharmaceuticals, on the safety and progress of the trial;

- Make recommendations concerning continuation, termination or other modifications of the trial based on the observed beneficial or adverse effects of the treatment under study; and
- If applicable, review interim analyses in accordance with stopping rules, which are clearly defined in advance of data analysis and have the approval of the DSMB.

11 Ethics

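### The plan gives the DSMB treatment codes only on request after a safety issue and provides no routine by-arm safety review, which does not fit the board's task in section 10

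*Protocol*

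**What the plan says.** **Access to codes (protocol 4.4.7).** The section names as aware of assignments "Only the pharmacist and the unblinded monitor responsible for performing drug accountability". Its general rule is: "The randomization assignment should not be revealed before the study has been completed and the database has been cleaned and closed". The DSMB's route is: "Data may be unblinded at the request of the DSMB to the study Medical Monitor in the event that a safety issue arises", qualified by "for which they determine there is a need to review the subject's treatment assignment". After such an unblinding, "If data is unblinded for any reason, the DSMB will not share the treatment assignment with the Sponsor"; an exception is allowed on medical or ethical grounds.

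**The board's task (protocol 10).** Besides weighing risk against benefit, the DSMB is to "Make recommendations concerning continuation, termination or other modifications of the trial based on the observed beneficial or adverse effects of the treatment under study". It also reviews interim analyses under predefined stopping rules, if applicable. Neither document contains a stopping rule.

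**What is planned during the trial.** Protocol 7.4 describes one look, after the first 95 FAS patients have had their follow-up visit: "Only a sample size re-estimation will be carried out during this interim analysis; no other statistical analyses will be conducted". SAP 1.4 says the same. An independent unblinded statistician does that work.

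**What reaches the board.** For SAE reports, protocol 6.2.2.1 says that the "CMO will notify the DSMB as appropriate". The AE tables by treatment group in SAP 4.5 belong to the final analysis, which under SAP 4.9 follows database lock and unblinding.

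**The concern.** A beneficial or adverse effect of treatment is a difference between arms. Followed as written, 4.4.7 makes pooled review the default, and codes are opened only in reaction to something the board has already noticed. That is circular for the signal that matters most. An excess on active drug of events that are frequent after this surgery would itself be the safety issue, yet nothing in the pooled data need draw attention to it.

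Protocol Table 1 lists bleeding, chest re-exploration, reintubation, arrhythmias and vasopressin infusion among the events associated with the operation, so a single case is unlikely to look like a drug effect. The protocol also names signals that need a by-arm view. Section 1.5 reports postoperative bleeding as an SAE in 2 L-citrulline patients of the pilot study and says these types of event will be monitored. It also reports hypotension in 2 of 11 L-citrulline and 1 of 11 placebo patients in CIT-002-01.

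At stake is how early an excess of serious events in children on bypass would be recognised.

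**Working it through.** The plan gives no figure on this point, so there is none to reproduce. The check sets the passages side by side and then illustrates what pooled counts hide.

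**1. Passages.**

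| Question | Where | Answer |
|---|---|---|
| Must the board judge treatment effects? | Protocol 10 | Yes |
| When may it see codes? | Protocol 4.4.7 | On its request, once a safety issue has arisen |
| What unit is named? | Protocol 4.4.7 | A subject's assignment |
| Otherwise? | Protocol 4.4.7 | Closed until the database is closed |
| Scheduled by-arm or A/B safety tables, meeting schedule, statistician serving the board? | Protocol and SAP | None found |

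**2. The same pooled count fits very different splits.** Take 95 patients as 48 versus 47 (an assumed near-equal split) and the section 1.5 hypotension rates. Expected events under 2/11 versus 1/11: 48 × 2/11 + 47 × 1/11 = 8.73 + 4.27 = 13.0. Under a common rate of 3/22: 95 × 3/22 = 12.95. The totals do not tell the two situations apart. Thirteen events could divide as follows (two-sided Fisher p):

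| L-citrulline / placebo | p |
|---|---|
| 7 / 6 | 1.00 |
| 10 / 3 | 0.070 |
| 11 / 2 | 0.014 |
| 13 / 0 | 0.0001 |

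**3. How often each kind of review would raise a flag.** Assumed rates, since the documents give no background rate for such an event: 30% on active and 10% on placebo. Expected events: 48 × 0.30 = 14.4 and 47 × 0.10 = 4.7, total 19.1, or 20% pooled.

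- By-arm rule: Fisher exact test at one-sided 5%. Exact power is 0.738.
- Pooled rule: flag if the total exceeds the 95th percentile of Binomial(95, b), where b is the background rate the board believes. The total is the sum of Binomial(48, 0.30) and Binomial(47, 0.10).

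| Believed background b | Flag if total exceeds | Probability of a flag |
|---|---|---|
| 10% | 15 | 0.829 |
| 15% | 20 | 0.348 |
| 20% | 26 | 0.028 |

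Both rules are nominal 5%; because counts are discrete, actual false-flag rates are lower.

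**4. Smaller excesses, same rules.**

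| Active vs placebo | By arm | Pooled, b = 10% / 15% / 20% |
|---|---|---|
| 25% vs 10% | 53% | 62% / 15% / 0.5% |
| 20% vs 10% | 30% | 35% / 4% / 0.05% |

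The pooled rule does slightly better than the by-arm test when the background is known to be 10%, and falls away quickly when it is believed to be higher. The by-arm comparison needs no such belief, because the placebo arm supplies the reference.

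**The case against.** A reader might infer from 4.4.7 that the DSMB cannot see an imbalance, or is prevented from doing its job. The text does not support that. The board itself decides when there is a need, nothing caps its requests, and the section expects it to hold assignments once they are opened. A board worried by a cluster of deaths or bleeding events could ask for every code in the cluster and see the split. For the same reason it does not follow that a signal would stay hidden until all 190 children had been treated.

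Three further readings also go too far. Section 7.4 limits what is done at the sample size look; it does not forbid DSMB safety review. The sentence about the CMO concerns SAE notification, not the content of board meetings. The list of people aware of assignments is not exhaustive, since 7.4 has its own unblinded statistician, and the reference to a subject's assignment may be generic.

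A DSMB charter outside these documents may also provide by-arm reports; neither document cites one.

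On the numbers, all event rates are assumed, tripling from 10% to 30% is a large excess, and pooled review is no worse when the background rate is known.

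All of this stands and narrows the point. What remains is that the only written access is reactive, that the general rule closing the codes carries no exception for routine DSMB reports, and that the signal most in need of comparison is the one least likely to prompt a request.

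**Conclusion.** The point holds as a mismatch between the written blinding rule and the board's charge, and it should be corrected. The protocol and SAP make no provision for routine by-arm safety review, while section 10 expects recommendations that rest on a comparison of arms.

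The size depends on how well the background rate is known. Under the assumed 30% versus 10% at 48 versus 47, by-arm review flags the excess 74% of the time. Pooled review ranges from 83% down to 3% as the believed background moves from 10% to 20%. These figures illustrate the mechanism; they do not forecast this trial. The conclusion also assumes that no charter already supplies closed by-arm reports. If one does, the remaining fault is that 4.4.7 as written conflicts with it.

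**What to change.** - **4.4.7:** keep the on-request sentence as an additional route. Add that the DSMB receives closed safety reports by coded arm, and make these an explicit exception to the rule that assignments stay closed until database closure.
- **10:** set a schedule of closed sessions, including one at the 95-patient look. At each, the independent unblinded statistician of 7.4 gives the DSMB, and nobody else, deaths, SAEs, refractory hypotension and bleeding events by arm, labelled A and B with the key available to the board.
- **7.4 (and SAP 1.4):** state that these tables are separate from the sample size re-estimation, are not an efficacy analysis and use no alpha.
- **Charter:** if a DSMB charter already provides such reports, cite it and align 4.4.7 with it.

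The cost is protocol and charter wording plus a small set of tables from a statistician already planned. Sample size and significance level are unchanged. The downside is that a few more independent people hold treatment codes.
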